### 7.4 STUDY INTERVENTION/EXPERIMENTAL MANIPULATION ADHERENCE

Adherence in this study is easy to assess in that GogyUp has internal data indicating users' interactions with the Reader app across its functionalities, including timestamps, functionality or activity used, and whether a user conducted a reading activity

successfully. We will assign study numbers so that adherence data can be linked to other study data later (while maintaining participant confidentiality). We will be able to assess the degree to which intervention adherence (regular or continued use of the GogyUp Reader app) has occurred and whether this may explain differences found or not found between the intervention and control arms.

## 7.5 CONCOMITANT THERAPY

As noted above regarding exclusions, we do not have any exclusions for concomitant therapy— only for the exclusions listed above and for being part of any treatment or intervention study.

### 7.5.1 RESCUE THERAPY

N/A

## 8 STUDY INTERVENTION/EXPERIMENTAL MANIPULATION DISCONTINUATION AND PARTICIPANT DISCONTINUATION/WITHDRAWAL

### 8.1 DISCONTINUATION OF STUDY INTERVENTION/EXPERIMENTAL MANIPULATION

Other than participant withdrawal (self-decided for any reason), we do not have any specific circumstances that would lead us to discontinue participants from the study. Because the intervention is a mobile app that participants will use on a self-directed, as-needed basis, it will be available to participants regardless of moves, or other changes in circumstance. In the case of adverse events, we would not revoke a participants' access to the app, but it could mean issues with loss to follow up, which we will address below.

### 8.2 PARTICIPANT DISCONTINUATION/WITHDRAWAL FROM THE STUDY

Participants are free to withdraw from participation in the study at any time upon request. As noted above, we have no explicit reasons, as the research team/investigators, to withdraw participants. We may of course have issues if people are highly non-adherent or we are not able to follow up with them, but we will address these as either empirical questions (see intervention adherence above) or analytically (see lost to follow-up below).

The reason for participant discontinuation or withdrawal from the study will be recorded in an electronic Case Report Form (CRF). Subjects who sign the informed consent form and are randomized but do not receive the study intervention may be replaced.

Subjects who sign the informed consent form, and are randomized and receive the study intervention, and subsequently withdraw, or are discontinued from the study, will not be replaced and lost to follow-up will be addressed analytically.

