#### 5.1.2 STUDY INTERVENTION:

The study intervention is the use of the GogyUp Reader app. The GogyUp Reader is a software app that can be used on mobile phones, tablets, and on PC's with any widely available, Chromium-based web browser (e.g., Google Chrome, Microsoft Edge, etc.). It is designed to provide both in-the-moment support for interacting with written materials, combined with activities designed to address overall functional adult literacy. This is intended to address personal capacity to deal with complex written patient education or care plan materials on an as-needed, low-cost/free and low-burden basis.

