### 6.4 SCREEN FAILURES

Screen failures are defined as participants who consent to participate in this study but are not subsequently assigned to the study intervention or entered in the study. Individuals who do not meet the criteria for participation in this trial (screen failure) because of meeting one or more exclusion criteria will not be rescreened.

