### 10.3 POPULATIONS FOR ANALYSES

Study population will include only intention-to-treat (as randomized).

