6	
Baseline Assessment & Onboarding
 
Research coordinator (RC) conducts the baseline assessment (remotely and preferably through Zoom video conference) of the Health Literacy Questionnaire (HLQ) with additional demographic questions for patient age in years, gender, self-identified race and ethnicity, and duration of diabetes diagnosis.
 
Before the participant signs-off, the RC will schedule and/or confirm the Follow-Up assessment, ideally scheduled close to any follow-up appointment the participant has scheduled with their provider.
 
The script for this step includes procedures for if the participant misses the appointment. After 3 attempts (or 4 attempts if we are towards the end of the recruitment phase), the RC will mark the participant as inactive and then mark the participant as “discontinued” if a new candidate is enrolled in the previous participant’s place.
 
If there is enough time and the participant has a mobile device, the RC will walk the participant through how to download GogyUp and create an account on their device or access GogyUp’s webapp.
	
Scripts:
 
 
• Baseline Assessment (Phone or Online Meeting)
 
• SMS Script – 1 Day Reminder
 
• Voice-mail – Missed Appointment
 
• SMS Script – Missed Appointment
 
 
Online Health Literacy Questionnaire (HLQ)
 
Online Demographic Questionnaire
				

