#### 15.6.6 MISSED BASE APPOINTMENT SCRIPTS AND PROCEDURE

If a participant misses a baseline appointment and is unresponsive to three contact attempts (mix of voice mail and SMS messages) sent in intervals of 2 days between messages, then mark the participant as “inactive” and move to enroll another candidate.

If another candidate is identified and attends the baseline appointment, then mark the inactive candidate as “replaced” in the participant database.

---

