## 15.6.7 INTERVENTION GROUP – ONBOARDING FOR GOGYUP READER

After the baseline assessment is completed, display the quick start guide (see section 15.7.2) and ask if the participant is ready to try GogyUp Reader.

If the participant does not have the time or access to an internet-connected device, explain that they will receive a quick start guide with their network access reimbursement. If they would like help with accessing the app, they are always welcomed to contact the research coordinators.

If the participant is ready and available, walk through these steps.

- 1) Point to step 1 in the Quick Start Guide and point out that the GogyUp Reader can be used on any Android or iOS device – or on a PC with a Chrome or Edge web browser.
- 2) Ask the participant which device they plan to use and verify they are able to find the GogyUp Reader on their device's app store (or through their browser).
- 3) Point to step 2 and state that the next step is to fill out a GogyUp profile. This information is used to sync progress so that if they want to use GogyUp on another device, they can.
  - a. Note that they don't have to use their real name.
  - b. For the **UserName** they should use their assigned **Study Number**.
- 4) Point to step 3 in the Guide and note that if the participant has a preferred language other than english, they may select from the options to have an individual word translated into that preferred language.
- 5) Point to step 4 and emphasize that the participant should put in “**ninr1**” in the invite code box – this is needed so that the participant has access to the content library for the study.
- 6) Guide the participant to tap “Save profile” and then point out the different features in the app:
  - a. **Points A&B** in the Guide's Features section: Touch any word to launch the “word menu”
    - i. Request that the word be spoken, defined, or translated.
    - ii. Point out the “hear sentence” button if the participant wants the entire sentence spoken.
    - iii. Note that some words will have a “practice” button – this is a quick, optional spelling activity and isn't related to the study.
  - b. **Point C:** Demonstrate how the EZText button can instantly re-format the text so that it fits better on smaller screens and enables individuals to focus on individual words and phrases. Point out how the participant can increase the font size.

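### Replacement of people already randomised, in 8.2 and the scripts, is not reconciled with the sole as-randomised ITT population

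*Combined protocol and SAP*

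**What the plan says.** **Section 8.2** has two rules. The first reads: "Subjects who sign the informed consent form and are randomized but do not receive the study intervention may be replaced". The second covers people who did receive the intervention and later leave: they "will not be replaced and lost to follow-up will be addressed analytically". Neither says what counts as receipt. Section 5.1.2 states "The study intervention is the use of the GogyUp Reader app"; 7.1.1 repeats this and describes control as the usual written materials without the app.

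**The scripts** use other triggers. In 11.1.4 Step 6, a participant who misses baseline and cannot be reached is made inactive, then *discontinued* "if a new candidate is enrolled in the previous participant’s place". Section 15.6.6 uses a different label, *replaced*, under the condition "If another candidate is identified and attends the baseline appointment". The notes in 15.6 apply the missed-baseline contact attempts to either group. Section 15.8.3 repeats the replacement procedure for a missed follow-up.

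**The analysis sections** point the other way. Section 10.3 reads "Study population will include only intention-to-treat (as randomized" and names no other population. Section 10.2 keeps people who withdraw or are lost in the analysis. Section 10.4.2 plans multiple imputation for a missing baseline value and last observation carried forward for attrition. None of these sections mentions replaced people.

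**The concern.** An as-randomised analysis needs everyone who was allocated. A rule that lets staff put one person in the place of another after allocation invites the trial team to count the newcomer and stop pursuing the original. If that happens, membership of each arm depends partly on what people did after learning their arm, and randomisation no longer protects either HLQ comparison or the PDSMS comparison.

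The coordinator who applies the rule is unblinded (7.3). Three-month outcomes that were never sought cannot be recovered at analysis, so the matter has to be settled in the protocol text.

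**Working it through.** **1. Order of events.** The arm is read from the sequence and shown to the participant at Step 5 (11.1.4; 15.5.1.1). Baseline may be done then or booked for later (15.5.1.4). Every replacement trigger below therefore falls after the arm is known.

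**2. The triggers side by side.**

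| Place | Trigger | Label | Arms |
|---|---|---|---|
| 8.2 | randomised, intervention not received | may be replaced | depends on the meaning of receipt |
| 11.1.4 Step 6 | baseline missed, no contact | discontinued | not restricted |
| 15.6.6 (with 15.6) | baseline missed, no contact | replaced | either |
| 15.8.3 | follow-up missed, no contact | replaced | not restricted |

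The last row contradicts the second rule of 8.2. It also contradicts 8.3 and 11.1.4 Step 8, which class the same person as lost to follow-up.

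**3. What receipt could mean.**

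- *Using the app* (5.1.2, 7.1.1). An app-arm participant with a completed baseline who never starts would meet the 8.2 trigger. This can happen: under 15.6.7, "If the participant does not have the time or access to an internet-connected device, explain that they will receive a quick start guide". Staff would see it in the daily activity reports of Step 7. Control has no clear equivalent, because controls never get the app and 7.1.2 says their activity cannot be measured.
- *Being sent access or materials.* A person in either arm who misses baseline would meet the trigger, because 15.7 provisions both arms after baseline and 15.6 posts control materials once baseline is confirmed. But 15.5.1.2 sends control materials at assignment, while 15.5.1.4 holds the app arm's tablet or data-plan compensation until after baseline. The moment of receipt is therefore not settled on this reading either.

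**4. What happens to the replaced person.** No section says that this person stays in the ITT set. Section 15.5.1.4 may book a follow-up at assignment, but no step says it is kept once a person who missed baseline is made inactive or replaced. Section 10.4.2 plans imputation for a missing baseline, which presupposes that such people remain; 15.6.6 treats them as swapped.

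**5. Arithmetic.** The plan's target power reproduces. With 80 per arm, difference 0.3, SD 0.74 and two-sided 5%: (0.3/0.74) × √(80/2) = 0.405 × 6.325 = 2.564, and Φ(2.564 − 1.960) = 72.7% (72.2% with the t distribution), against 73% stated in 10.2. The sample-size calculation is not at issue.

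Let q be the share of an arm that is replaced and left out of the analysis, and d the amount in SD by which those people would have scored below the people kept. The app-minus-control difference then shifts by

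q(app) × d(app) − q(control) × d(control).

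The documents give none of the four inputs. The shift is zero if replaced people are kept as 10.3 requires, zero if the two products are equal, and of either sign otherwise.

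As an illustration only, assume no controls are replaced, the app has no effect, q(app) is 5% to 20% and d(app) is 0.25 to 0.75. The shift runs from 0.05 × 0.25 = 0.0125 SD to 0.20 × 0.75 = 0.15 SD, and two-sided type I error at 80 per arm from about 5.1% to 15.8%. This ignores baseline adjustment. If the gap is the same at baseline and follow-up, ANCOVA multiplies the shift by about (1 − ρ). With ρ assumed at 0.5 to 0.7, the range becomes 0.0125 × 0.3 = 0.004 SD to 0.15 × 0.5 = 0.075 SD. These figures are not an estimate for this trial: the result depends entirely on the assumed inputs.

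**The case against.** The strongest reply is that the documents already treat app non-use as something to keep. Section 8.2, just before the replacement sentence, handles high non-adherence as an empirical or analytical matter. Section 2.1 lets users choose whether to use the app, 7.1.2 requires no level of use, and 5.3 calls low use under ITT a finding. Step 7 answers an inactive account with a contact about access, not a replacement. No script replaces a non-installer, and a non-starter with a baseline has a follow-up that nothing cancels. All of this stands. It weakens the app-use reading of 8.2 but does not close it, because receipt remains undefined.

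Four stronger readings are tempting, and the documents do not support them:

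- *App-arm non-starters are removed while control has no counterpart.* The missed-baseline procedure covers either group, and under 15.6 and 15.7 a control who misses baseline is not sent the packet. The schedule in 2.3 also lists the control and experimental interventions together.
- *Replaced people are excluded from analysis.* Section 8.2 says they may be replaced, and a strict reading of 10.3 keeps them. The defect is an unresolved conflict that permits removal.
- *The newcomer inherits a known arm.* Only the Step 6 phrase suggests this. Section 7.3 and Step 5 send each new participant to the sequence, and 15.6.6 applies its label only once the newcomer has attended baseline, a step that follows allocation.
- *Someone lost after assignment becomes a screen failure.* Section 6.4 defines these as "participants who consent to participate in this study but are not subsequently assigned to the study intervention or entered in the study". Read that literally, every control would be one, so the wording cannot bear the inference.

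The procedure in 15.8.3 closely tracks 15.6.6 and may be a drafting carry-over. It is nonetheless in force as written.

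**Conclusion.** The conflict is real and should be fixed. Section 8.2 and three script passages permit replacement after randomisation, with the arm known, under triggers and labels that disagree. Nothing ties replaced people back to the as-randomised population in 10.3 or to the missing-data methods in 10.4.2. The two clearest defects are the missed-follow-up swap in 15.8.3 and the absence of a follow-up step for people replaced after a missed baseline.

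The documents do not show that the HLQ comparisons are biased towards the app. Neither direction nor size can be derived, because they give no non-starter rate, no replacement rate by arm and no prognostic gap. If 10.3 is applied to the letter and outcomes are sought from everyone, the problem does not arise. The conclusion rests on what the text allows, not on any assumed magnitude.

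**What to change.** 1. Delete the replacement sentence in 8.2, and the *discontinued*/*replaced* swaps in 11.1.4 Step 6, 15.6.6 and 15.8.3.
2. State in 8.2 and 10.3: *Everyone assigned an arm stays in the ITT population in that arm. The three-month HLQ and PDSMS are sought from all of them, whether or not they complete baseline, install the app or read the materials, unless consent is withdrawn.*
3. State in 7.3: *Any further recruit takes the next unused position in the allocation sequence and substitutes for nobody.*
4. Add a line to 10.4.2 for people with neither a baseline nor a follow-up value, since they have no observation to carry forward.

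The cost is protocol and script wording, plus contact attempts for people who would otherwise have been dropped. The number with complete data may fall slightly short of 160, or a few more people may need to be randomised, which the existing ceiling of 200 allows.

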### 8.3 LOST TO FOLLOW-UP

A participant will be considered lost to follow-up if contact fails for the three-month follow-up assessment and study staff are unable to contact the participant after at least 3 attempts using a mixture of voice calls and SMS texts, spaced over several days.

The following actions must be taken if a participant fails to attend or answer a follow-up research visit or call:

- Before a participant is deemed lost to follow-up, the research coordinator or study staff will make every effort to regain contact with the participant (where possible a mix of 3 telephone calls and text messages and, if necessary, a certified letter to the participant's last known mailing address or local equivalent methods). These contact attempts will be documented in a study file.
- Should the participant continue to be unreachable, he or she will be considered to have withdrawn from the study with a primary reason of "lost to follow-up."

## 9 STUDY ASSESSMENTS AND PROCEDURES

---

### 9.1 ENDPOINT AND OTHER NON-SAFETY ASSESSMENTS

Assessments for this study will include eligibility assessment and initial contact for pre-screening, as well as baseline and follow-up measures. We will also extract internal app data for the study period to assess adherence in the intervention arm (and to ensure no contamination in the control arm).

To ensure a focus on equitable representation and on a sample reflective of our interest in low income (publicly or non-insured) patients, the study team and health system research support staff determined that initial contact with recruiting materials (see above) will be prioritized to individuals seen at primary care clinics in the health system that see the largest proportions of publicly insured or non-insured patients. Iterative mailings will continue to prioritize patients from these clinics as well as patients in historically excluded and underrepresented groups (e.g., Black or Indigenous patients) among those fitting initial eligibility criteria (see above). Health system staff will conduct pre-screening procedures including identifying a potential sample and sending recruitment mailings (see Recruitment Collateral below). To ensure candidates are fully opted-in, GogyUp and study staff will not have access to any potential participants until participants contact GogyUp by filling out an online intake form or calling, texting, or emailing the GogyUp Research Coordinator through a study-designated phone number and email address listed on the recruitment letter.

Once eligible participants are consented by the GogyUp Research Coordinator, enrollment and baseline assessments will take place within an expected two-week (maximum) timeframe. Baseline assessments will include study staff administration (remotely via phone or video call) of the validated Health Literacy Questionnaire subscales 9 and 2, "Understanding health information" and "Having sufficient information," as well as the secondary outcome of the PDSMS. At three months post-baseline, study staff will conduct follow-up administration of the same outcomes. Based on our theoretical mechanism of action (see above), health literacy is the primary set of

outcomes, with diabetes self-management as the secondary outcome. Although we will conduct standard training and include standard scripts for study staff for the baseline and three-month follow-up appointments, study staff administering these assessments will not have specific training or degree requirements. They will use a time stamp of “time 0” for the baseline survey date.

## 9.2 SAFETY ASSESSMENTS

N/A

## 9.3 ADVERSE EVENTS AND SERIOUS ADVERSE EVENTS

As noted in 3.3.1, the primary risks to participants are a breach of data prior to assigning study numbers (rather than identifiable information) for individuals. Should a data breach occur, the research staff will respond according to GogyUp’s Privacy Policy and University of Minnesota procedures. These include notification of the data breach in accordance with the United States Department of Health and Human Services HIPAA Breach Notification Rule, 45 CFR §§ 164.400-414, section 13407 of the HITECH Act and the information previously reviewed in the Study Disclosure Document and Informed Consent Form.

Upon discovery of a breach, GogyUp technical staff will immediately evaluate data systems to identify the source of the leak and determine whether the vulnerability can be removed. If the vulnerability is determined to be a continued risk, then study enrollment and/or activity will be halted - dependent on which systems were impacted by the vulnerability, whether the vulnerability has been verified to have been removed and patches to the GogyUp’s data systems have been successfully implemented and tested, and if continuing the study would be in accordance with the University of Minnesota policies.

## 9.4 UNANTICIPATED PROBLEMS

### 9.4.1 DEFINITION OF UNANTICIPATED PROBLEMS

This protocol uses the definition of Unanticipated Problems as defined by the Office for Human Research Protections (OHRP). OHRP considers unanticipated problems involving risks to participants or others to include, in general, any incident, experience, or outcome that meets all of the following criteria:

- Unexpected in terms of nature, severity, or frequency given (a) the research procedures that are described in the protocol-related documents, such as the Institutional Review Board (IRB)-approved research protocol and informed consent form; and (b) the characteristics of the participant population being studied;
- Related or possibly related to participation in the research (“possibly related” means there is a reasonable possibility that the incident, experience, or outcome may have been caused by the procedures involved in the research); and

- Suggests that the research places participants or others at a greater risk of harm (including physical, psychological, economic, or social harm) than was previously known or recognized.]

---

#### 9.4.2 UNANTICIPATED PROBLEMS REPORTING

The investigator will report unanticipated problems (UPs) to the reviewing Institutional Review Board (IRB) and to the lead research co-principal investigator (Co-PI [name]). The UP report will include the following information:

- Protocol identifying information: protocol title and number, PI's name, and the IRB project number
- A detailed description of the event, incident, experience, or outcome
- An explanation of the basis for determining that the event, incident, experience, or outcome represents an UP
- A description of any changes to the protocol or other corrective actions that have been taken or are proposed in response to the UP

To satisfy the requirement for prompt reporting, UPs will be reported using the following timeline:

- UPs that are serious adverse events (SAEs) will be reported to the IRB and to the funding agency within 24 hours of the investigator becoming aware of the event
- Any other UP will be reported to the IRB and to the funding agency within 36 hours of the investigator becoming aware of the problem
- All UPs should be reported to appropriate institutional officials (as required by an institution's written reporting procedures), the supporting agency head (or designee), and the Office for Human Research Protections (OHRP) within 7 days of the IRB's receipt of the report of the problem from the investigator

---

